**b. Adverse Events**

Researchers will follow all ethical and professional reporting requirements for adverse events. Reporting of adverse events will occur as follows (procedures below are consistent with requirements of the Partners IRB):

1) Serious adverse events that are reportable according to the guidelines of the Office for Human

Research Protections (OHRP) and FDA (e.g., death, suicide attempt, inpatient hospitalization) will be reported by telephone within 2 business days to the IRB of MGH.

A full written report of the event will be sent to the MGH IRB within 1 week of the event's occurrence.

2) Any other unanticipated problems occurring will be reported to the IRB within 2 weeks, in accordance with guidelines of the Office for Human Research Protections (OHRP) and FDA.

3) All adverse events will be summarized in the PCORI and IRB annual progress reports.

## VIII. DATA ANALYSIS

Baseline demographic and clinical characteristics will be examined by the PI in collaboration with [name]., Professor of Biostatistics. Measures of central tendency and variability will be estimated on each continuous measure; proportions estimated for categorical variables. Transformations will be used when distributional assumptions are not fulfilled for inferential tests. Dropouts and completers will be compared on baseline variables using Mann-Whitney or chi-square tests. Following FDA guidance for clinical trials, we will not correct our single primary outcome for multiple comparisons. We have 61 additional secondary/exploratory analyses. These will be corrected for multiple comparisons using the Bonferroni method, which yields an alpha level of 0.0008.

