### A. Primary Aims

**Aim 1: To determine if 1) web-based CBT or web-based MBCT, supported by use of Fitbit technology for self-tracking of activity, improves physical activity, and 2) How these two therapies compare to a Fitbit-only control group.**

*Hypothesis 1a:* Because CBT (compared to MBCT) is the more directive intervention, we hypothesize that CBT will be superior to MBCT in increasing daily steps over the course of 8-weeks of treatment and at follow-up.

*Hypothesis 1b:* Both forms of therapy-based treatment will be superior to the Fitbit only control group in increasing daily steps over the course of 8-weeks of treatment and at follow-up.

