**III. INTERVENTION MODULES AND OVERVIEW**

Participants in both therapy-based interventions will access materials (e.g., client vignettes, videos, activities) that illustrate ways to increase physical activity (e.g., walks, runs, climbing stairs, etc.). They will be guided to gradually increase their daily steps (physical activity) at their own pace. Both CBT and MBCT will be provided online and will guide participants through the elements of each treatment which are geared to address the barriers against exercise that individuals with mood disorders at risk for or with CVD face (fear of the physiological signs of exertion as they may mean a heart attack, etc.). Besides structured guidance towards exercise, the main focus of both treatments will be on addressing these obstacles that prevent individuals from engaging in exercise. Participants in both of these groups will receive Fitbit devices to measure their steps (main outcome) throughout the study. In addition to the two treatment-based intervention group there will also be a group of participants who serve as controls. This group will receive a Fitbit device, but no form of therapy and will not have access to the online therapy material. By including this control group, we will be able to ensure that any treatment effect is not due to wearing a Fitbit.

**Cognitive-behavioral therapy (CBT):** CBT will be based on previous work using CBT to enhance exercise in individuals with mood disorders which includes the following elements: (1) identifying and setting realistic exercise-based goals and intermediate goals (to maximize success to increase motivation); (2) behavioral scheduling to optimize when to exercise, identify rewards for exercising, and problem solve obstacles to exercising; and (3) identify dysfunctional, maladaptive thoughts about exercise (which decrease motivation) and skills to identify more adaptive, positive thoughts (to overcome thoughts of being too tired or too stressed to exercise). These aspects follow the core components of CBT, or to change dysfunctional thoughts and behaviors to change a problem behavior (i.e., sedentary behavior). Evidence shows that adjunctive CBT for exercise helps patients improve their planning to exercise, motivation to exercise, and self-efficacy (or one's belief in their ability) to exercise. Two hundred participants will be randomized to this group.

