### B. **Statistical Analyses Plan for Research Aims**

Each of the statistical tests below will use a two-tailed alpha-level of 0.05.

**Aim 1: Hypothesis 1a and 1b:** *CBT will be superior to MBCT in increasing daily steps over the course of 8-weeks of treatment and after 8 additional weeks of follow-up, and both forms of treatment will be superior to the Fitbit-only, control group.* The primary hypothesis, or Hypothesis 1a, is that the CBT group will do better than the MBCT group at increasing the number of daily steps. A secondary hypothesis, or Hypothesis 1b, is that the CBT and MBCT groups will do better at increasing the number of steps as measured by the FitBit over the 16-week study compared to the FitBit-only group. Since the data for Hypotheses 1a and 1b both use repeated measures on subjects, we will conduct analyses for both hypothesis using general linear mixed models that account for the covariance of observations within subjects. For both hypotheses, we will model a random intercept and slope for subjects and site and fixed effects for treatment, time, and potentially confounding covariates. The treatment by time interaction for both hypotheses will be used to assert the statistical significance of treatment effects. Canonical links will be used to correctly model the distribution of dependent variables: for count data (e.g. steps) Poisson regression

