models will be fit with the Poisson family and the log link and for normally distributed data linear regression models will be fit with the Gaussian distribution and identity link. To choose the correct model for the hypotheses, we will use the Shapiro-Wilk test to assess for normality as well as the deviance statistic, the Akaike information criterion and the Bayesian information criterion to assess the best fitting model. We will compare nested models with the likelihood ratio chi-square statistics for both hypotheses. When a treatment effect is significant for either Hypothesis 1a or 1b, we will clarify its clinical significance by computing, for each time point, effect size statistics that convey the magnitude of treatment group differences. For effect size of both hypotheses, we will use the standardized mean difference for continuous variables. Our primary analyses for Hypotheses 1a and 1b will use daily steps as measured by Fitbit (primary outcome), and then self-reported physical activity, weight, perceived stress, PHQ-9, Altman Mania Scale Scores, and Sheehan disability scores as secondary outcome measures

**Aim 2: Exploratory Aims (Phase II).** *Hypotheses:* Between treatment group effects sizes (and 95% CI) will be calculated. To supplement this, Mann-Whitney tests will compare treatment groups on medical burden (as measured by FRS) (*Hypothesis 2a*) and on improvement in symptoms (PHQ-9, ASRM) and functioning (SDS) (*Hypothesis 2b*) based on change from baseline.

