### D. Power Analysis

Following FDA guidance for clinical trials, we will not correct our single primary outcome for multiple comparisons. We have 61 additional secondary/exploratory analyses. These will be corrected for multiple comparisons using the Bonferroni method, which yields an alpha level of 0.0008.

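### Hypothesis 1b on daily steps has no settled place in the multiplicity plan: its secondary label puts it at 0.0008 among 61 analyses, section VIII.B puts it at an uncorrected 0.05, and neither serves it well

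*Combined protocol and SAP*

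**What the plan says.** Section II.A (Primary Aims) lists Hypothesis 1b: "Both forms of therapy-based treatment will be superior to the Fitbit only control group in increasing daily steps". Section III explains why the Fitbit-only arm exists: "By including this control group, we will be able to ensure that any treatment effect is not due to wearing a Fitbit".

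Section VIII.B then ranks the two hypotheses. On 1a: "The primary hypothesis, or Hypothesis 1a, is that the CBT group will do better than the MBCT group". On 1b: "A secondary hypothesis, or Hypothesis 1b, is that the CBT and MBCT groups will do better at increasing the number of steps".

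The multiplicity rule is in the opening paragraph of section VIII and is repeated in VIII.D. The exemption reads "we will not correct our single primary outcome for multiple comparisons". Everything else falls under "We have 61 additional secondary/exploratory analyses. These will be corrected for multiple comparisons using the Bonferroni method, which yields an alpha level of 0.0008". The 61 analyses are not listed, and there is no hierarchy, gatekeeping or key-secondary tier.

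Two statements in VIII.B point the other way for 1b. Its first sentence sets a two-sided 0.05 for all the tests that follow, 1b among them. Later it says "Our primary analyses for Hypotheses 1a and 1b will use daily steps as measured by Fitbit (primary outcome"), which treats the step analysis of 1b as primary.

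**The concern.** Hypothesis 1a compares two active programmes. Whichever way it falls, it cannot show that either programme adds anything to the device; only 1b can. A plan that lists 1b under its primary aims and randomises 100 people to answer it should say at what level it is tested.

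Read by label, 1b has the same weight as each of the other analyses in the 61, apparently including the exploratory Aim 2 tests. Tests with no confirmatory role would then use up the alpha of the trial's most important secondary question. Read by the first sentence of VIII.B, 1b is tested at 0.05 with no allowance for two contrasts or for the tests around it. An analyst could defend either level after seeing the data, and a p-value between 0.0008 and 0.05 would be a success under one and a failure under the other.

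**Working it through.** **The plan's own figure.** 0.05/61 = 0.00082, which rounds to the stated 0.0008. The two-sided critical value rises from 1.960 at 0.05 to 3.353 at 0.0008.

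**Inputs from the documents.** 200 CBT, 200 MBCT and 100 Fitbit-only (section III); 20% attrition (VIII.C), so 160, 160 and 80 if every dropout is a complete loss. VIII.D contains no effect size, SD or target power.

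**Assumptions.** Normal approximation on a standardised mean difference d; the same true d for both therapies; d shown as a range. The planned treatment-by-time mixed model is not simulated.

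**Per-contrast power.** SE = sqrt(1/160 + 1/80) = 0.137, and power = Φ(d/SE − critical value). For d = 0.4, d/SE = 2.921, giving Φ(0.961) = 83.2% at 0.05 and Φ(−0.432) = 33.3% at 0.0008.

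| d | 0.05 | 0.0008 |
|---|---|---|
| 0.3 | 59.1% | 12.3% |
| 0.4 | 83.2% | 33.3% |
| 0.5 | 95.5% | 61.7% |
| 0.6 | 99.2% | 84.8% |

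Half the power is lost at d/SE = 3.223, that is d = 0.44, where power is 90% at 0.05 and 45% at 0.0008. Above that, the loss is under half. The effect detectable with 80% power is (1.960 + 0.842) × 0.137 = 0.38 at 0.05 and (3.353 + 0.842) × 0.137 = 0.57 at 0.0008.

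For any approximately normal test statistic, 80% power at 0.05 becomes Φ(1.960 + 0.842 − 3.353) = 29% at 0.0008.

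**Sensitivity to sample size.** With no loss to attrition (200 v 100), SE = 0.122: d = 0.4 gives 90% v 46%, and d = 0.5 gives 98% v 77%. If 1b were one pooled contrast (320 v 80), d = 0.4 gives 89% v 44%.

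**Both therapies superior.** The shared control gives the contrasts a correlation of (1/80)/(1/160 + 1/80) = 0.667. Flat 0.0008 is compared with Holm on the two contrasts at familywise 0.05 (bivariate normal and simulation):

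| d | Both: Holm | Both: 0.0008 | At least one: Holm | At least one: 0.0008 |
|---|---|---|---|---|
| 0.3 | 44% | 6% | 61% | 19% |
| 0.4 | 74% | 21% | 86% | 45% |
| 0.5 | 92% | 49% | 97% | 75% |

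**The 0.05 reading.** With both nulls true, two uncorrected contrasts give 1 − P(|Z1| < 1.96 and |Z2| < 1.96) at correlation 0.667, about 8.5%, before any other secondary test is counted.

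**Error control of a hierarchy.** Take one therapy as clearly effective, the other null, and the lower tier null, independent and using its full alpha.
- Holm with its second step at 0.05, and 0.025 also passed down after a single success, spends the same 0.025 twice: 0.05 + 0.95 × 0.025 = 7.4%.
- Opening the lower tier only when both contrasts succeed holds the error at 5.0%.
- Fixing both contrasts at 0.025 and passing 0.025 per success also holds: 0.025 + 0.975 × 0.025 = 4.9%. Power for both is then 35%, 65% and 87% at d = 0.3, 0.4 and 0.5.

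**The case against.** The strongest objection is that 1b may not be in the family at all. No sentence places it there by name, and the 61 are not itemised. The exemption is worded by outcome, not by hypothesis, and daily steps under 1b is that outcome. The 0.05 sentence stands directly above 1b. A reader might infer that the plan definitely tests 1b at 0.0008; the documents do not support that, because membership follows only from the word secondary. The same caution applies to the Aim 2 tests: their place in the 61 is inferred from the combined secondary/exploratory wording. This part of the objection stands. It does not remove the problem: if the 0.05 sentence governed everything in VIII.B, the Bonferroni rule would have almost nothing left to act on, and 1b would lack error control.

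A second objection is that the loss is conditional. A reader might infer that 1b loses most of its power whatever the effect. At d = 0.5, 62% remains per contrast and 75% for at least one therapy. Treating all attrition as complete loss is also pessimistic, because a repeated-measures model uses partial data and VIII.C keeps assessing non-compliers. Both points stand, and the range above reflects them.

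Third, a flat Bonferroni family is valid, and naming a single primary hypothesis is legitimate. That is correct: 0.0008 is a costly choice for 1b, not an invalid one.

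**Conclusion.** The concern holds in a limited form. The documents give Hypothesis 1b two incompatible significance levels, and neither suits the question the control arm is there to answer. At 0.05 throughout, its two contrasts and the other secondary tests are uncorrected. At 0.0008, power to show both therapies superior is 6%, 21% and 49% for d of 0.3, 0.4 and 0.5, against 44%, 74% and 92% if 1b were tested first by Holm.

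These sizes rest on 160 v 80, a normal approximation, equal effects of the two therapies and an assumed d. They do not support saying that the trial cannot answer the second half of Aim 1: for d above about 0.44, or with less effective attrition, 1b keeps more than half its per-contrast power even at 0.0008. The plan should be changed before the data are analysed.

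**What to change.** Amend the multiplicity text in the opening of section VIII and in VIII.D, and the alpha sentence at the start of VIII.B, so that all three say the same:

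1. Keep Hypothesis 1a at two-sided 0.05.
2. Within the 0.05 already allotted to the secondary analyses, test Hypothesis 1b on daily steps first, as two contrasts (CBT + Fitbit v Fitbit-only, MBCT + Fitbit v Fitbit-only), by Holm at familywise 0.05: the smaller p-value against 0.025, then the other against 0.05.
3. Only if both contrasts are significant, test the remaining secondary analyses by Bonferroni at 0.05 over their own itemised count. Otherwise report them with estimates and confidence intervals and no significance claim.
4. Pass no alpha down after a single success. If the sponsor wants that option, fix both 1b contrasts at 0.025 in advance and accept the lower power for both (35%, 65% and 87%).
5. Take the Aim 2 analyses out of the count and report them as exploratory, as their heading already describes them.

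This needs wording only, with no new data or participants. The cost is that the other secondary results become descriptive unless both 1b contrasts succeed, and that Aim 2 carries no significance claims. The change leaves the plan's separate 0.05 for 1a and 0.05 for the secondary family as they are.

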**Fitbit-Only Control Group:**

Participants assigned to the Fitbit-only control study group you will not be receiving therapy. However, they will receive a Fitbit, which they will be asked to wear over the course of 16 weeks as well as to complete the same schedule of assessments as the therapy arms. One hundred participants will be randomized into this group.

Participation in this study can be added to an individual's regular course of treatment (such as medications) but should not replace ongoing treatment with his/her own doctor. Throughout participation in this study, the participant should continue any medications or treatments that his/her own doctor feels will best treat the symptoms of depression and/or cardiovascular disease.

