### C. Rate of Attrition

Some attrition (i.e., 20%) is expected and this can result in bias and reduce power, precision and generalizability. Consistent with the Intent to Treat principle, we will continue with the assessments for the study duration, even among those who fail to comply with the treatment.

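### Bonferroni at 0.0008 for the 61 secondary and exploratory analyses is valid, but Holm's step-down procedure is at least as powerful at the same familywise level; the expected gain is small

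*Combined protocol and SAP*

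**What the plan says.** The opening paragraph of section VIII (Data Analysis) puts the primary outcome outside the correction: "Following FDA guidance for clinical trials, we will not correct our single primary outcome for multiple comparisons". It then counts the rest, "We have 61 additional secondary/exploratory analyses", and gives the rule: "These will be corrected for multiple comparisons using the Bonferroni method, which yields an alpha level of 0.0008". Section VIII.D (Power Analysis) repeats these sentences. A single level for every test means single-step Bonferroni. No step-down procedure is mentioned, no reason for the choice is given, and the 61 analyses are not listed.

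Section VIII.B opens with a different level: "Each of the statistical tests below will use a two-tailed alpha-level of 0.05". The tests below that sentence include Hypothesis 1b, which the section calls secondary, and the secondary outcomes (self-reported activity, weight, perceived stress, PHQ-9, Altman mania, Sheehan disability). For Aim 2 the same section adds interval estimates: "Between treatment group effects sizes (and 95% CI) will be calculated".

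**The concern.** Single-step Bonferroni holds all 61 tests to the cutoff that only the smallest p-value needs. Once one hypothesis has been rejected, at most 60 true null hypotheses can remain, and the next p-value can be compared with 0.05/60 without raising the familywise error. The plan does not use that slack.

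At stake is power for the secondary results. The secondary outcomes are related, are compared across three arms and are mostly measured repeatedly, so several real effects may appear together, and that is when a step-down procedure gains most. If Hypothesis 1b belongs to the 61, which the plan does not say, the comparison with the Fitbit-only group would also be held to 0.0008, with only 100 participants randomized to that group.

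**Working it through.** **Inputs from the plan.** Family of 61 and level 0.0008 (section VIII opening and VIII.D). Two-sided 0.05 (VIII.B), taken here as the familywise level because the plan states none for the 61 tests and 0.05 reproduces its figure. 200 participants in each therapy arm (section III: "Two hundred participants will be randomized to this group") and 20% attrition (VIII.C: "Some attrition (i.e., 20%) is expected"), hence 200 × 0.8 = 160 per therapy arm.

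**Assumed, because the plan gives no values.** The number of true effects, their size, and the correlation between tests.

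**1. The plan's figure.** 0.05/61 = 0.00082, which is 0.0008 to four decimals. 61 × 0.0008 = 0.0488, below 0.05. The stated level is reproduced and is safe.

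**2. Holm's thresholds.** After k rejections the next p-value is compared with 0.05/(61 − k).

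| Rejections so far | Threshold |
|---|---|
| 0 | 0.00082 |
| 1 | 0.00083 |
| 5 | 0.00089 |
| 10 | 0.00098 |
| 20 | 0.00122 |
| 40 | 0.00238 |
| 60 | 0.05 |

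**3. No rejection is lost.** Every threshold is at least 0.05/61. A p-value at or below 0.05/61, and every p-value smaller than it, therefore passes under Holm too.

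**4. Error control is the same.** Suppose m0 null hypotheses are true. Before the first false rejection at most 61 − m0 hypotheses have been rejected, so the threshold then is at most 0.05/m0. The chance that any of m0 true nulls has a p-value that small is at most m0 × 0.05/m0 = 0.05, whatever the dependence between tests.

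**5. Power per test.** Two means, standardized effect 0.4, 160 per arm:

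| Level | Power |
|---|---|
| 0.05, uncorrected | 94.7% |
| 0.05/61 (Bonferroni, or Holm's first comparison) | 59.2% |
| Holm after 5 rejections | 60.1% |
| Holm after 10 | 61.1% |
| Holm after 20 | 63.4% |

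The correction costs 94.7 − 59.2 = 35.5 points. Holm recovers 0.9, 1.9 and 4.2 of them after 5, 10 and 20 rejections.

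**6. Chance that Holm adds anything.** Simulation of 61 two-sided z-tests, 20,000 trials per setting, correlation 0.3, true effects at z = 3.5, both methods using unrounded 0.05/61:

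| True effects | At least one extra rejection |
|---|---|
| 3 to 5 | about 1-2% |
| 10 | about 9% |
| 20 | about 34% |
| 30 | about 63% |

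Setting Bonferroni at the rounded 0.0008 while Holm uses unrounded thresholds gives about 12%, 37% and 65% for 10, 20 and 30 true effects. The 2 to 3 extra points come from rounding, not from stepping down.

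**7. Mean number of true findings.** Standardized effect 0.4, 160 per arm, correlation 0, both unrounded:

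| True effects | Bonferroni | Holm |
|---|---|---|
| 3 | 1.78 | 1.78 |
| 6 | 3.54 | 3.58 |
| 10 | 5.93 | 6.03 |
| 20 | 11.84 | 12.31 |
| 40 | 23.7 | 26.0 |

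The gain is 0.1 of a finding or less with up to 10 true effects. Across standardized effects of 0.3 to 0.5 and correlations of 0 and 0.5, Holm lost no Bonferroni rejection. Its familywise error stayed at or below 0.05 apart from simulation noise (highest 0.0504, with no true effects, where Bonferroni gave the same).

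**The case against.** The strongest reply is that nothing here is wrong. Bonferroni is valid, the arithmetic is correct, the analyses are labelled secondary or exploratory, and the primary conclusion is untouched. That stands, and it makes this an efficiency point and not a fault.

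A reader might go further and infer that the plan gives up findings with nothing in return. The documents do not support that. A single-step rule gives one cutoff known in advance that does not depend on the other 60 p-values. It also has simple matching simultaneous intervals, at 100 × (1 − 0.05/61) = 99.92% each. The second advantage goes unused here, because the plan states 95% intervals and claims no simultaneous coverage. The fixed cutoff is a real convenience.

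Nor is there a case that rounding to 0.0008 wastes alpha: it is ordinary rounding to four decimals.

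Some of Holm's extra rejections may be false. In runs at z = 3.5 and correlation 0.3, realised familywise error rose from 3.4% to 3.9% with 10 true effects and from 2.0% to 3.1% with 30. Both stay under 0.05, so the guarantee is the same, but the realised rate is not identical.

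Finally, Holm needs the family fixed in advance, and the plan does not list the 61 analyses. Bonferroni needs the same list to justify dividing by 61, so this does not favour either method.

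**Conclusion.** The point holds as an optional improvement. Holm at familywise 0.05 is at least as powerful as the planned rule, with the same nominal error control and no added assumption; that part is a mathematical result and needs no trial data.

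The size of the gain does rest on assumptions. It is close to nil if only a handful of the 61 effects are real, and becomes noticeable only when a large share are. Most of the power lost on these tests comes from controlling familywise error over a family of 61, and Holm returns only a few points of it. Related outcomes make clusters of real effects plausible, but the documents give no effect sizes or correlations from which to infer a large gain.

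The conflict between 0.05 in section VIII.B and 0.0008 elsewhere in section VIII has to be resolved whichever procedure is kept. Low priority.

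**What to change.** In the opening paragraph of section VIII and again in VIII.D, replace the fixed 0.0008 cutoff with wording such as: *The 61 secondary and exploratory analyses will be tested by Holm's step-down procedure at a two-sided familywise level of 0.05, and Holm-adjusted p-values will be reported.* List the 61 analyses so that the family is prespecified, and say whether Hypothesis 1b is among them. In VIII.B, limit the per-test two-tailed 0.05 to the primary test. Make the change before any unblinded analysis.

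The change of procedure costs one sentence in two places and one line of code, with no extra data. Listing the family is additional work, but Bonferroni needs it as well. What is given up is the single fixed cutoff and the simple matching simultaneous intervals. Adjusted p-values can be read directly against 0.05, which makes up for much of the first; the plan does not use the second.
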